### 3.5.11 Dabrafenib-Trametinib Dose Modification for Hypertension

Increases in blood pressure (BP) have been observed in patients receiving dabrafenib plus trametinib. Recommendations for BP monitoring and management are provided below.

Monitoring: All BP assessments should be performed under the following optimal conditions:

- The subject has been seated with back support, ensuring that legs are uncrossed and flat on the floor.
- The subject is relaxed comfortably for at least 5 minutes.
- Restrictive clothing has been removed from the cuff area, and the right cuff has been selected.
- The subject's arm is supported so that the middle of the cuff is at heart level.
- The subject remains quiet during the measurement.
- In subjects with an initial BP reading within the hypertensive range, a second reading should be taken at least 1 minute later,

with the two readings averaged to obtain a final BP measurement. The averaged value should be recorded in the eCRF.

- Visits to monitor increased blood pressure can be scheduled independently from the per-protocol visits outlined in the study calendar. Ideally, subsequent blood pressure assessments should be performed within 1 week.
- Persistent hypertension is defined as an increase of systolic BP (SBP) > 140 mmHg and/or diastolic BP (DBP) > 90 mmHg in three consecutive visits with blood pressure assessments from two readings.
- Asymptomatic hypertension is defined as an increase of SBP > 140 mmHg and/or diastolic BP (DBP) > 90 mmHg in the absence of headache, light-headedness, vertigo, tinnitus, episodes of fainting, or other symptoms indicative of hypertension.

Dabrafenib-Trametinib Treatment Modification for Hypertension		
Event	Management Guideline	Dose Modification
(Scenario A) Asymptomatic and persistent a SBP of $\geq 140$ and $< 160$ mmHg, or DBP $\geq 90$ and $< 100$ mmHg OR • Clinically significant increase in DBP of 20 mmHg (but DBP still below 100 mmHg)	• Adjust current or initiate new antihypertensive medication(s). • Titrate antihypertensive medication(s) during the next 2 weeks to achieve well-controlled b BP. • If BP is not well-controlled within 2 weeks, consider referral to a specialist and go to scenario (B).	• Continue study treatment.
(Scenario B) Asymptomatic SBP $\geq 160$ mmHg, or DBP $\geq 100$ mmHg, OR • Failure to achieve well-controlled BP within 2 weeks in Scenario A.	• Adjust current or initiate new antihypertensive medication(s). • Titrate antihypertensive medication(s) during the next 2 weeks to achieve well-controlled BP.	• Interrupt study treatment if clinically indicated. • Once BP is well-controlled b , restart study treatment reduced by one dose level c .
(Scenario C) Symptomatic d hypertension OR • Persistent SBP $\geq 160$ mmHg, or DBP $\geq 100$ mmHg, despite antihypertensive medication and dose reduction of study treatment	• Adjust current or initiate new antihypertensive medication(s). • Titrate antihypertensive medication(s) during the next 2 weeks to achieve well-controlled BP. • Referral to a specialist for further evaluation and follow-up is recommended.	• Interrupt study treatment • Once BP is well controlled, restart study treatment reduced by one dose levelc .
(Scenario D) Refractory hypertension unresponsive to above interventions or hypertensive crisis.	Continue follow-up per protocol.	• Permanently discontinue study treatment.
a. Hypertension detected in two separate readings during up to three consecutive visits b. Well-controlled blood pressure defined as SBP $\leq 140$ mm Hg and DBP $\leq 90$ mm Hg in two separate readings during up to three consecutive visits. c. Escalation of trametinib to previous dose level can be considered if BPs remain well-controlled for 4 weeks after restarting of trametinib. Approval from the subprotocol Study Chair is required. d. Symptomatic hypertension defined as hypertension aggravated by symptoms (e.g., headache, light-headedness, vertigo, tinnitus, episodes of fainting) that resolve after the blood pressure is controlled within the normal range		

Rev. 8/15

### 3.5.12 Dabrafenib-Trametinib Dose Modification for QTc Prolongation

Dabrafenib - Trametinib modification for QTc Prolongation	
QTc Prolongation a	Action and Dose Modification
• QTcB $\geq$ 501 msec	
 
Interrupt study treatment until QTcB prolongation resolves to grade 1 or baseline.
 
Test serum potassium, calcium, phosphorus and magnesium. If abnormal, correct per routine clinical practice to within normal limits.
 
Review concomitant medication usage for agents that prolong QTc.
 
If the event resolves, restart study treatment at current dose levelb.
 
If the event does not resolve, permanently discontinue study treatment. Consider evaluation with cardiologist.
 
If the event recurs, permanently discontinue study treatment. Consider evaluation with cardiologist.
 

Abbreviations: msec = milliseconds; QTcB = QT interval on electrocardiogram corrected using the Bazett's formula
 
a) Based on average QTc value of triplicate ECGs. For example, if an ECG demonstrates a prolonged QT interval, obtain two or more ECGs over a brief period, and then use the averaged QTc values of the three ECGs to determine if study treatments should be interrupted or discontinued.
 
b) If the QTc prolongation resolves to grade 1 or baseline, the subject may resume study treatment if the subprotocol Study Chair agrees that the subject will benefit from further treatment.
	

Rev. 8/15

### 3.5.13 Dabrafenib-Trametinib Dose Modification for Diarrhea

Episodes of diarrhea have been observed in patients receiving dabrafenib, trametinib, or both therapies in combination. Other, frequent causes for diarrhea including concomitant medications (e.g., stool softeners, laxatives, antacids, etc.), infections caused by *C. difficile* or other pathogens, partial bowel obstruction, etc., should be clinically excluded.

Dabrafenib-Trametinib Treatment Modification and Management Guidelines for Diarrhea		
CTCAE Grade	Management Guideline	Action and Dose Modification
Uncomplicated Diarrhea,  Grade 1 or 2	
 
Diet: Stop all lactose containing products; eat small meals, BRAT-diet (banana, rice, apples, toast) recommended.
 
Hydration: 8-10 large glasses of clear liquids per day (e.g., Gatorade or broth).
 
Loperamide: Initially 4 mg, followed by 2 mg every 4 hours or after every unformed stool; maximum 16 mg/day. Continue until diarrhea-free for 12 hours.
 
Diarrhea > 24 hours: Loperamide 2 mg every 2 hours; maximum 16 mg/day. Consider adding oral antibiotics.
 
Diarrhea > 48 hours: Loperamide 2 mg every 2 hours; maximum 16 mg/day. Add budesonide or other second-line therapies (octreotide, or tincture of opium) and oral antibiotics.
 
	
 
Continue study treatment.
 
If diarrhea is grade 2 for > 48 hours, interrupt study treatment until diarrhea resolves to grade ≤ 1.
 
Restart study treatment at the same dose level.
 

Uncomplicated Diarrhea,  Grade 3 or 4  Any Complicated Diarrhea 	
 
Clinical evaluation mandatory.
 
Loperamide: Initially 4 mg, followed by 2 mg every 4 hours or after every unformed stool; maximum 16 mg/day. Continue until diarrhea-free for 12 hours.
 
Oral antibiotics and second-line therapies if clinically indicated
 
Hydration: Intravenous fluids if clinically indicated.
 
Antibiotics (oral or intravenous) if clinically indicated.
 
Intervention should be continued until the subject is diarrhea-free for ≥ 24 hours.
 
Intervention may require hospitalization for subjects at risk of life-threatening complications.
 
	
 
Interrupt study treatment until diarrhea resolves to ≤ grade 1.
 
Restart study treatment reduced by one dose level.
 
If 3 dose reductions of study treatment are clinically indicated, permanently discontinue study treatment.
 

 
1. Uncomplicated diarrhea defined by the absence of symptoms such as cramping, nausea/vomiting, ≥ grade 2, decreased performance status, pyrexia, sepsis, neutropenia ≥ grade 3, frank bleeding, and/or dehydration requiring intravenous fluid substitution.
 
2. Complicated diarrhea defined by the presence of symptoms such as cramping, nausea/vomiting, ≥ grade 2, decreased performance status, pyrexia, sepsis, neutropenia ≥ grade 3, frank bleeding, and/or dehydration requiring intravenous fluid substitution.
 
3. Loperamide should be made available prior to start of study treatment so loperamide administration can begin at the first signs of diarrhea.
 
4. Escalation of study treatment to previous dose level is allowed after consultation with the subprotocol Study Chair and in the absence of another episode of complicated or severe diarrhea in the 4 weeks subsequent to dose reduction.
 
		

Rev. 8/15

### 3.5.14 Dabrafenib-Trametinib Dose Modification for Visual Changes

Episodes of visual changes have been observed in patients receiving dabrafenib, trametinib, or the combination of both therapies. An ophthalmologist should be consulted if changes in vision develop. However, if the visual changes are clearly unrelated to study

Rev. 8/15

treatment (e.g., allergic conjunctivitis), then monitor closely as it may be reasonable to defer ophthalmic examination.

Uveitis and iritis have been associated with dabrafenib, while RPED and RVO have been associated with trametinib therapy. Monitor patients for visual signs and symptoms (such as change in vision, photophobia, and eye pain) during therapy. Special attention should be given to retinal findings (e.g., retinal pigment epithelial detachment (RPED) or retinovascular abnormalities (i.e., branch or central retinal vein occlusions [RVO])).

The ophthalmology exam will include best corrected visual acuity, visual field examination, tonometry, slit lamp biomicroscopic examination of the anterior segment (with special attention to inflammation) and the posterior segment, and dilated indirect funduscopy with special attention to retinal abnormalities. Optical coherence tomography is strongly recommended at scheduled visits and if retinal abnormalities are suspected. Other types of ancillary testing including color fundus photography, and fluorescein angiography may also be indicated as determined by clinical exam.

Guidelines regarding event management and dose reduction for visual changes considered to be related to study treatment are provided in the table below.

Dabrafenib-Trametinib Treatment Modification for Visual Changes		
CTCAE Grade	Management Guideline	Action and Dose Modification
Grade 1*	
 
Consult ophthalmologist within 7 days of onset.
 
	
 
If dilated fundus examination cannot be performed within 7 days of onset, hold trametinib until RPED and RVO can be excluded by retina specialist/ ophthalmologist. Dabrafenib may be continued.
 
If RPED and RVO excluded, continue (or restart) trametinib at same dose level
 
If Uveitis/Iritis, refer to table below for Iritis/Uveitis
 
If RPED suspected or diagnosed, refer to RPED dose modification table below; report as SAE if diagnosed.
 
If RVO diagnosed: Permanently discontinue trametinib and report as SAE.
 

Grade 2 and Grade 3	
 
Consult ophthalmologist immediately.
 
	
 
Hold trametinib. Dabrafenib may be continued.
 
If RPED and RVO excluded, restart trametinib at same dose level after visual AE is <math>\leq</math> grade 1. If no recovery within 4 weeks, discontinue trametinib.
 
If Uveitis/Iritis, refer to table below for Uveitis/Iritis
 
If RPED diagnosed, see RPED dose modification table below; report as SAE.
 
If RVO diagnosed: Permanently discontinue trametinib and report as SAE.
 

Grade 4	
 
Consult ophthalmologist immediately.
 
	
 
Interrupt trametinib. Dabrafenib may be continued.
 
If RPED and RVO excluded, may consider restarting trametinib at same or reduced dose after discussion with the subprotocol Study Chair.
 
If Uveitis/Iritis, refer to table below
 
If RVO or RPED diagnosed, permanently discontinue trametinib and report as SAE.
 

Abbreviations: RPED = retinal pigment epithelial detachments; RVO = retinal vein occlusion; SAE = serious adverse event
 
*If visual changes are clearly unrelated to study treatment (e.g., allergic conjunctivitis), monitor closely but ophthalmic examination is not required.
		

Rev. 8/15

Dabrafenib-Trametinib Dose Modification for RPED	
Event CTCAE Grade	Action and Dose Modification
Grade 1 RPED (Asymptomatic; clinical or diagnostic observations only)	
 
Continue trametinib with retinal evaluation monthly until resolution. If RPED worsens, follow instructions below.
 
Dabrafenib treatment is not affected
 

Grade 2-3 RPED (Symptomatic with mild to moderate decrease in visual acuity; limiting instrumental ADL)	
 
Interrupt trametinib. Continue dabrafenib
 
Retinal evaluation monthly.
 
If improved to <math>\leq</math> Grade 1, restart trametinib with one dose level reduction or discontinue in patients taking trametinib 1 mg daily.
 
If no recovery within 4 weeks permanently discontinue trametinib
 

Dabrafenib-Trametinib Dose Modification for Uveitis and Iritis	
CTCAE Grade	Action and Dose Modification
Uveitis and Iritis	
 
Continue study treatment
 
Control ocular inflammation with local therapies
 
If not improved to grade <math>\leq 1</math> within 1 week, interrupt dabrafenib until resolution of ocular inflammation and then restart dabrafenib reduced by one dose level
 
If no recovery within 4 weeks, permanently discontinue dabrafenib. Trametinib may be continued.
 

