Hyperbilirubinemia	15	0	7	4	0	0
Chemistry						
Hyperglycemia	58	5	67	6	49	2
Hyponatremia	55	11	48	15	36	2
Hypophosphatemia	47	5	41	11	40	0
Increased creatinine	24	5	20	2	9	0
a NCI CTCAE v4. b Includes the following terms: peripheral edema, edema, and lymphedema. c Includes the following terms: rash, rash generalized, rash pruritic, rash erythematous, rash popular, rash vesicular, rash macular, rash maculo-papular. d Includes the following terms: brain stem hemorrhage, cerebral hemorrhage, gastric hemorrhage, epistaxis, gingival hemorrhage, hematuria, vaginal hemorrhage, hemorrhage intracranial, eye hemorrhage, and vitreous hemorrhage. e Includes the following terms: renal failure and renal failure acute.						

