		Palmar-plantar erythrodysesthesia syndrome	
	Pruritus		Pruritus (Gr 2)
		Skin and subcutaneous tissue disorders - Other (drug reaction with eosinophilia and systemic symptoms [DRESS])	
Skin and subcutaneous tissue disorders - Other (rash) 			Skin and subcutaneous tissue disorders - Other (rash) (Gr 3)

Adverse Events with Possible Relationship to Trametinib (CTCAE 5.0 Term) [n= 1111]			Specific Protocol Exceptions to Expedited Reporting (SPEER)
Likely (>20%)	Less Likely (<=20%)	Rare but Serious (<3%)	
		Stevens-Johnson syndrome 	
VASCULAR DISORDERS			
	Hypertension		Hypertension (Gr 3)
		Thromboembolic event (venous)	
	Vascular disorders - Other (hemorrhage) 		

 This table will be updated as the toxicity profile of the agent is revised. Updates will be distributed to all Principal Investigators at the time of revision. The current version can be obtained by contacting [[contact]](mailto:[contact]). Your name, the name of the investigator, the protocol and the agent should be included in the e-mail.

 Atrioventricular block includes Atrioventricular block complete, Atrioventricular block first degree, Mobitz type II atrioventricular block.

 Bundle branch block includes Bundle branch block right and Bundle branch block left, Conduction disorder; Mobitz type I.

 Visual disorders include visual disturbance that can be associated with, conjunctival hemorrhage, corneal graft rejection, cyclitis, eye nevus, halo vision, iritis, macular edema, retinal hemorrhage, visual acuity reduced, visual impairment, and vitreous detachment.

 Generalized edema includes edema, lymphedema, and edema limbs.

 Hypersensitivity (allergic reactions) may present symptoms such as fever, rash, increased liver function tests, and visual disturbances.

 Hemophagocytic lymphohistiocytosis is observed in combination with dabrafenib which also has this adverse event.

 Tumor lysis syndrome: Cases of tumor lysis syndrome, including fatal cases, have been reported in patients treated with trametinib in combination with dabrafenib.

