 Skin and subcutaneous tissue disorders - Other (rash) may include rash, rosacea, rash acneiform, erythematous rash, genital rash, rash macular, exfoliative rash, rash generalized, erythema, rash papular, seborrheic dermatitis, dermatitis psoriasiform, rash follicular, skin fissures, and skin chapped.

 Stevens-Johnson syndrome has been observed in patients treated with trametinib and dabrafenib combination.

 The majority of hemorrhage events were mild. Major events, defined as symptomatic bleeding in a critical area or organ (e.g., eye, GI hemorrhage, GU hemorrhage, respiratory hemorrhage), and fatal intracranial hemorrhages have been reported.

**Adverse events reported on trametinib trials, but for which there is insufficient evidence to suggest that there was a reasonable possibility that trametinib caused the adverse event:**

**BLOOD AND LYMPHATIC SYSTEM DISORDERS** - Disseminated intravascular coagulation; Febrile neutropenia; Leukocytosis

**CARDIAC DISORDERS** - Atrial fibrillation; Cardiac arrest; Cardiac disorders - Other (cardiac stenosis); Myocardial infarction; Restrictive cardiomyopathy; Sinus tachycardia

**EAR AND LABYRINTH DISORDERS** - Hearing impaired

**ENDOCRINE DISORDERS** - Hypothyroidism

**EYE DISORDERS** - Corneal ulcer; Eyelid function disorder; Flashing lights; Floaters; Glaucoma; Photophobia

**GASTROINTESTINAL DISORDERS** - Abdominal distension; Ascites; Colonic ulcer; Duodenal ulcer; Esophageal necrosis; Esophageal ulcer; Esophagitis; Gastric ulcer; Gastritis; Gastroesophageal reflux disease; Gastrointestinal disorders - Other (abdominal visceral perforation); Gastrointestinal disorders - Other (bowel obstruction); Gastrointestinal disorders - Other (pneumatosis intestinalis); Gastrointestinal disorders - Other (parotid gland swelling); Gastrointestinal fistula; Gingival pain; Ileus; Obstruction gastric; Pancreatitis; Small intestinal obstruction

**GENERAL DISORDERS AND ADMINISTRATION SITE CONDITIONS** - Death NOS; Flu-like symptoms; Gait disturbance; General disorders and administration site conditions - Other (axillary pain); General disorders and administration site conditions - Other (systemic inflammatory response syndrome); Localized edema; Malaise; Non-cardiac chest pain; Pain; Sudden death NOS

**HEPATOBIILIARY DISORDERS** - Bile duct stenosis; Cholecystitis; Hepatic failure; Hepatic pain; Hepatobiliary disorders - Other (hepatic encephalopathy)

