#### **Dabrafenib and Trametinib Dose Modification Guidelines**

If an AE resolves to grade 1 or baseline at the reduced dose level, and no additional toxicities are seen after 4 weeks of study treatment at the reduced dose, the dose may be increased to the previous dose level. A dose reduction below 50 mg BID for dabrafenib is not allowed. For dabrafenib-trametinib combination, dose below 1 mg once daily for trametinib is not allowed; however, if dabrafenib will be permanently discontinued for dabrafenib-related toxicities, the patients will be allowed to continue trametinib. Conversely, if trametinib is permanently discontinued for trametinib-related toxicities, patients will be allowed to continue dabrafenib.

The dose modifications may involve one or both agents, and should be based on the nature, severity and attributions of the AEs. General guidelines are provided in Tables below, with details stipulated in subsequent sections. The CTEP drug monitors should be consulted if there are questions about the attribution of AEs and how the doses should be modified.

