#### 3.5.6 Dabrafenib-Trametinib Dose Modification for Hemorrhages

Dabrafenib-Trametinib Treatment Modifications for Hemorrhage	
Grade 3	Hold dabrafenib-trametinib for up to 2 weeks If improved, resume the drugs at one dose reduction If no improvement, permanently discontinue dabrafenib-trametinib
Grade 4	Permanently discontinue dabrafenib or dabrafenib-trametinib

- 
- 3.5.7      Dabrafenib-Trametinib Dose Modification for Pancreatitis
- In the event of abdominal pain or suspected pancreatitis, amylase and lipase laboratory samples should be collected for confirmation of the diagnosis. Patients should be closely monitored when re-starting dabrafenib after an episode of pancreatitis. For changes in treatment, please refer to *Dose Modification for Toxicities Not Specified in Subsequent Sections* Section [3.5.1](#)
- 3.5.8      Dabrafenib-Trametinib Dose Modification for Hyperglycemia
- Hyperglycemia requiring an increase in the dose of, or initiation of insulin or oral therapy can occur with dabrafenib. Monitor serum glucose levels as clinically appropriate during treatment with dabrafenib in subjects with pre-existing diabetes or hyperglycemia. Advise patients to report symptoms of severe hyperglycemia such as excessive thirst or any increase in the volume or frequency of urination. For changes in treatment, please refer to *Dose Modification for Toxicities Not Specified in Subsequent Sections* Section [3.5.1](#)
- 3.5.9      Dabrafenib-Trametinib Dose Modification for Renal Insufficiency
- Cases of renal insufficiency have occurred in patients receiving the combination of dabrafenib and trametinib. Prior to start of study treatment, concomitant medications should be reviewed for the potential risk of inducing nephrotoxicity and modified if clinically possible.

Rev. 8/15

Dabrafenib-Trametinib Dose Modification for Renal Insufficiency		
Serum Creatinine Level	Management Guideline	Action and Dose Modification
Serum creatinine increase > 0.2 mg/dL (18 mcmmol/L) BUT ≤ 0.5 mg/dL (44 mcmmol/L) above baseline	
 
• Recheck serum creatinine within 1 week.
 
• Serum creatinine increase >1 week: contact the subprotocol Study Chair. If elevation persists beyond 4 weeks, recommend evaluation (consider renal biopsy) for etiology; consider nephrology consultation.
 
• If pyrexia is present, treat pyrexia as per guidelines.a
 
	Continue study treatment at the same dose level.

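### After a treatment-related grade 3 eye bleed with RPED and RVO excluded, Section 3.5.6 resumes trametinib one dose level lower but Section 3.5.14 restarts it at the same level, and the protocol does not say which table governs

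*Protocol*

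**What the plan says.** **Section 3.5.6 (hemorrhages), grade 3.** Both drugs are held for up to 2 weeks. Then: "If improved, resume the drugs at one dose reduction". Without improvement, both drugs stop for good. No bleeding site is excluded.

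**Section 3.5.14 (visual changes), grade 2 and 3 row.** The table covers "dose reduction for visual changes considered to be related to study treatment". Trametinib is held, dabrafenib may go on, and an ophthalmologist is consulted at once. Then: "If RPED and RVO excluded, restart trametinib at same dose level after visual AE is" grade 1 or lower. Without recovery in 4 weeks, trametinib stops. The row names uveitis/iritis, RPED and RVO and either redirects or handles each. It has no branch for a bleed.

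**General text in Section 3.5.** Dose changes "should be based on the nature, severity and attributions of the AEs", and questions go to the CTEP drug monitors. There is also a floor: for the combination, a "dose below 1 mg once daily for trametinib is not allowed".

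**The concern.** A severe bleed in the eye that disturbs vision is both a hemorrhage and a visual change. Each table gives a complete, directive instruction for restarting trametinib, and the two differ by one dose level. A site that opens only the visual-change table finds an answer and has no prompt to look further.

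The looser instruction is the less safe one: it returns the patient to the full previous trametinib dose after a grade 3 bleed, where the hemorrhage table requires a reduction. This is a dosing-safety matter. It does not touch the response-rate estimate or its confidence interval.

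**Working it through.** The check compares the two rules, asks whether one event can fall under both, and looks for a ranking. The only arithmetic is on the dose levels and one percentage.

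**1. Can one event fall under both tables?**
- Section 1.7, footnote d of the combination adverse-event table, counts these among the hemorrhage terms: "hemorrhage intracranial, eye hemorrhage, and vitreous hemorrhage".
- Section 3.3, footnote 11 of the trametinib list, describes major bleeding as "symptomatic bleeding in a critical area or organ (e.g., eye" and other named sites).
- Section 3.3, footnote 4 of the same list, ties visual disorders to a set of findings that includes "macular edema, retinal hemorrhage, visual acuity reduced, visual impairment, and vitreous detachment".

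So the protocol's own vocabulary places eye bleeding under hemorrhage and also associates it with visual disorders. These are term-grouping footnotes. They show that the overlap is possible but do not set the scope of a dosing table.

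**2. What restart dose does each table give?** The trametinib levels in Section 3.5 are 2, 1.5 and 1.0 mg once daily.

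| Dose before the event | Section 3.5.6 | Section 3.5.14, grade 2 and 3 row | 3.5.6 relative to 3.5.14 |
|---|---|---|---|
| 2 mg | 1.5 mg | 2 mg | 1.5/2 = 0.75, i.e. 25% lower |
| 1.5 mg | 1.0 mg | 1.5 mg | 1.0/1.5 = 0.667, i.e. 33% lower |
| 1.0 mg | no permitted level | 1.0 mg | cannot resume versus resume |

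**3. Is there a ranking?** Section 3.5.1 applies only to toxicities that no later section covers, so it does not order 3.5.6 against 3.5.14. The general paragraph in Section 3.5 points to the nature of the event and to consultation. Section 1.7 lists hemorrhages and ocular events as separate events of special interest. Both lean towards 3.5.6, but neither says which table prevails. Elsewhere the protocol does cross-refer: Sections 3.5.7 and 3.5.8 send the reader to 3.5.1, and the renal table in 3.5.9 sends the reader to 3.5.2.

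**4. Can a frequency be derived?** Three figures in Section 1.7, all from the earlier combination arm at 150/2, come close.
- Grade 3 and 4 hemorrhage is given as 5% of 55. Since 2/55 = 3.6%, 3/55 = 5.5% and 4/55 = 7.3%, this is 3 patients.
- Intracranial or gastric bleeds are also 3/55. The counts match, but the text does not say that they are the same patients.
- The only ocular event above grade 2 was one grade 3 RPED. Because hemorrhages are listed apart from ocular events, an eye bleed may not have been counted there.

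The figures are compatible with no severe eye bleed in that arm, but they do not establish it and give no rate.

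**The case against.** The strongest reply is that ordinary reading settles the case. Section 3.5.14 works as a symptom-driven work-up: hold trametinib, consult the ophthalmologist, find the cause. Once the cause is a grade 3 bleed, the event is by nature a hemorrhage and the section of that name applies. The footnotes used to show the overlap classify terms, one of them for an earlier melanoma trial, and do not assign bleeds to the visual-change table. In doubt, the CTEP drug monitors are available.

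Much of this stands. Most clinicians would probably follow the diagnosis, and the text leans that way. It does not remove the conflict, because the visual-change row does not otherwise leave diagnoses to inference. It names three causes and says what to do for each, and a bleed is the branch left out. Consultation helps only a site that sees a question to ask.

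Two stronger readings are tempting but not supported.
- A reader might infer that the tables also clash on dabrafenib or on grade 4 events. In Section 3.5.14, dabrafenib may continue, and after a grade 4 event a trametinib restart at the same or a reduced dose may be considered with the Study Chair. That wording is permissive, so the stricter hemorrhage rule can be followed without breaching it.
- A reader might infer that patients in this trial have been dosed wrongly. The protocol shows no such case.

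**Conclusion.** The point holds in narrow form. For a treatment-related grade 3 ocular hemorrhage with a grade 2 or 3 visual change, and with RPED and RVO excluded, the two tables give trametinib restart doses one level apart. At 1 mg, one table restarts the drug while the other leaves no permitted dose. The protocol indicates the likely intended table without saying that it governs.

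This rests on two assumptions: that an eye bleed with visual change is read as falling under both tables, and that the MATCH Master Protocol, not available here, has no precedence rule. Practical weight is low. The event is expected to be rare, no rate can be derived, and Section 1.9 closes accrual on December 31, 2022, so only patients still on treatment could be affected; their number is not given. The response-rate analysis is unaffected. The change is optional but worthwhile, since the possible error is towards a higher dose after a severe bleed.

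**What to change.** Add one branch to the grade 2 and 3 row of Section 3.5.14:

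> *If a grade 3 ocular hemorrhage is diagnosed, follow Section 3.5.6 (including its 2-week limit and one-level dose reduction) instead of the same-dose restart; if RVO or RPED is also diagnosed, the stricter instruction applies to each drug.*

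Naming the 2-week limit matters because the visual-change row allows 4 weeks for recovery, and a patient whose bleed has improved may still have impaired vision. The last clause is needed because the grade 2-3 RPED row continues dabrafenib while Section 3.5.6 holds it, and because a diagnosed RVO ends trametinib permanently. The grade 4 row needs no change.

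The cost is one sentence in the next addendum, with no new assessments. The trametinib risk list in Section 3.3 carries a July 25, 2025 version date, so the document was still being maintained and an addendum is a realistic vehicle.

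### In section 3.5.14 the dabrafenib action for uveitis or iritis does not depend on grade at onset, so as written a grade 3–4 event continues dabrafenib for up to a week

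*Protocol*

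**What the plan says.** Section 3.5.14 of the protocol has three linked tables.

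- **Visual changes, by grade.** At grade 1 an ophthalmologist is consulted within 7 days. At grades 2–4 the instruction is "Consult ophthalmologist immediately". At grade 2–3 the drug action is "Hold trametinib. Dabrafenib may be continued"; at grade 4 it is "Interrupt trametinib. Dabrafenib may be continued". Every row refers uveitis and iritis to a separate table. Once retinal pigment epithelial detachment (RPED) and retinal vein occlusion (RVO) are excluded, the grade 2–3 row says to "restart trametinib at same dose level after visual AE is" grade 1 or less. The grade 4 row makes a restart subject to discussion with the Study Chair.
- **RPED, by grade.** At grade 2–3: "Interrupt trametinib. Continue dabrafenib". For grade 4 the visual-changes table says: "If RVO or RPED diagnosed, permanently discontinue trametinib and report as SAE".
- **Uveitis and iritis.** The first column is headed as a CTCAE grade, but the only row carries just the event name. The first action is "Continue study treatment", with local therapy. If the event has not reached grade 1 or less, the instruction continues "within 1 week, interrupt dabrafenib until resolution of ocular inflammation and then restart dabrafenib reduced by one dose level". Without recovery by 4 weeks, dabrafenib stops permanently and trametinib may go on.

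The text above these tables associates uveitis and iritis with dabrafenib, and RPED and RVO with trametinib.

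**The concern.** The dabrafenib rule turns on persistence at one week. A mild iritis and a grade 4 uveitis get the same first-week instruction for dabrafenib, the drug the section links to the event. The only drug action that varies with grade falls on trametinib. The general guidance in section 3.5 names severity, with nature and attribution, as a basis for dose changes, and section 1.7 shows that grade 3 and grade 4 uveitis have occurred on the combination.

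The row also gives an instruction that cannot be followed together with its parent table: one continues study treatment, which means both drugs, while the other holds trametinib at grades 2–4. A site cannot tell which governs.

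What is at stake is patient safety and consistent handling across sites. No estimate, interval or decision rule for response depends on it.

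**Working it through.** The protocol gives no figure to reproduce. The check has two parts: following the rule, and sizing the event.

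**1. Following a grade 3 or 4 uveitis**

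- Visual-changes table: immediate ophthalmology consultation; trametinib held; dabrafenib may continue; go to the uveitis table.
- Uveitis table: continue study treatment with local therapy; interrupt dabrafenib only if the event is still above grade 1 after one week.
- No step makes the dabrafenib action depend on grade at onset.

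**2. Comparison with the default**

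Section 3.5.1 covers toxicities without a section of their own. It interrupts treatment at grade 3, and permanently discontinues or interrupts at grade 4. A restart is one dose level lower after resolution to grade 1 or baseline. In the first week, therefore, a severe toxicity that the protocol did not foresee gets a stricter rule than severe uveitis, which it did.

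**3. How often this could arise**

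Inputs from section 1.7: two grade 3 cases and one grade 4 case of uveitis; 365 combination-treated subjects, of whom 2% had uveitis, iritis or iridocyclitis. The text does not tie the three cases to the 365, so that denominator is an assumption.

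- Rate: 3/365 = 0.82%, exact (Clopper-Pearson) 95% CI 0.17% to 2.38%.
- Share of these events that were severe: 2% after rounding means 0.015 × 365 = 5.5 to 0.025 × 365 = 9.1, so 6 to 9 patients. If the three cases are among them, 3/9 = 33% to 3/6 = 50%.
- Part C 150/2 group (n = 55): all ocular events were grade 1–2 except one grade 3 RPED, so there was no grade 3–4 uveitis. For 0/55 the exact 95% CI is 0% to 6.5%. At a true rate of 0.82%, the chance of none is (1 − 0.00822)^55 = 0.635. This group neither confirms nor excludes the rate.
- Accrual goal of 85: 85 × 0.00822 = 0.70 expected cases (0.14 to 2.03 over the CI). This is an upper bound, because accrual was to stop on December 31, 2022 (section 1.9) and a change now affects only patients still on treatment.
- Patients still on treatment: the number is not given. Assuming 5 to 20, 5 × 0.00822 = 0.04 to 20 × 0.00822 = 0.16 expected cases.

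These figures count severe events. They do not measure harm from a one-week delay, on which the protocol has no data.

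**The case against.** The strongest reply is that treating uveitis by its response to local therapy is a legitimate clinical choice.

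- **Evidence for local therapy.** Section 1.7 reports that these events responded to symptomatic therapy, mainly topical corticosteroids, in the same paragraph as the grade 3–4 cases. This supports local therapy as the first step. It does not give response by grade or say whether dabrafenib was held, so it does not settle the severe cases.
- **Other safeguards.** Immediate ophthalmology consultation is required at grades 2–4. Section 3.7 ends treatment for unacceptable toxicity, and directs stopping at any time if the constraints of the protocol are detrimental to the patient's health. These reduce the risk, but they rest on the investigator's judgement and do not require a dabrafenib hold at a given grade.
- **Other rules not set by grade.** Pyrexia is managed by episode, and severity is only one of three factors in the general guidance. So an ungraded rule is not in itself an error.
- **RPED differs in kind.** The protocol gives no local therapy for it, so the comparison shows only that the section can grade a drug-linked eye event.

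A reader might infer more than the protocol supports:

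- That 3.5.14 ignores severity altogether. It does not: it grades the consultation and the trametinib hold, and the uveitis row has a grade threshold at one week.
- That the row contradicts 3.5.1. It does not, because 3.5.1 excludes toxicities specified later.
- That a patient with grade 4 uveitis is bound to a week of dabrafenib. Section 3.7 and the permissive wording of the visual-changes table say otherwise.
- That a longer hold would trigger the two-week removal rule. Section 3.5 already exempts interruptions for visual changes with recovery, and the uveitis table sits under that heading.

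**Conclusion.** The point holds in a narrow form. For uveitis and iritis, the written dabrafenib action is the same at every grade for the first week and is weaker at grade 3–4 than the protocol's own default. The row also conflicts with the trametinib hold at grades 2–4.

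This is a minor point and a cheap safety improvement. On the assumed denominator of 365, about 0.8% of patients would have such an event (95% CI 0.2% to 2.4%): at most about 0.7 expected cases in 85 patients, and 0.04 to 0.16 if 5 to 20 remain on treatment. That the delay causes injury is not shown. Sample size, precision and the response-rate analysis are unaffected.

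**What to change.** Split the row by grade.

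- **Grade 1–2:** leave dabrafenib as written.
- **Grade 3:** interrupt dabrafenib at diagnosis with local therapy. Restart one dose level lower after the ocular inflammation has resolved. Discontinue permanently if there is no recovery within 4 weeks.
- **Grade 4:** permanently discontinue dabrafenib, or interrupt it on the same restart terms and 4-week limit. This follows the choice offered in 3.5.1.
- **Trametinib:** add one line saying that the instruction to continue study treatment does not override the hold in the visual-changes table, whose restart conditions stay as they are.

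The two-week removal rule needs no change.

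The cost is wording in one table, with no added visits or tests. The patient who loses is the rare one with a grade 3–4 event who would have reached grade 1 or less within a week and so kept full-dose dabrafenib. That patient would miss dabrafenib until resolution and might be off both drugs at once. The restart is at 100 mg instead of 150 mg BID, and section 3.5 allows re-escalation after 4 weeks at the lower dose. The reduced period costs 28 × (1 − 100/150) = 9.3 full-dose days. With a 7-day hold the total is 7 + 9.3 = 16.3 days, and with a 28-day hold 28 + 9.3 = 37.3 days. Permanent discontinuation at grade 4 costs all later dabrafenib.
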